6.3.2 Strategies to improve adherence and procedure to monitor adherence.

1. 1. Direct questioning by the PI about the application of the IP.
2. 2. Delivery of a printed calendar specifying the date of the visit and its activities.
3. 3. Journal of the subject.

6.3.2.1 Procedure to monitor adherence.

For more than four decades, there have been numerous investigations on the proper way to measure and quantify adherence to medications, however none has reached consensus to establish itself as the gold standard, both in cross-sectional and longitudinal studies. [48, 49, 50, 51, 52, 53, 54, 55]

There are different procedures to measure the adherence of pharmacological interventions. The most common procedure includes self-reports, these include: patient interviews, questionnaires and self-monitoring journals. Its strengths are speed, flexibility, low cost and ease of implementation; they have a high degree of specificity for non-adherence, nevertheless, the sensitivity and reliability for adherence is low. [55, 56]

The biochemical measurement of the drug, or its metabolite, is one of the methods that best confirms the use of the drug. Nevertheless, in addition to raising costs and being impractical, it is of little use in the context of ophthalmic applications, since concentrations at the peripheral level could be undetectable; and samples from other tissues imply more invasive methods that would not be advisable. [55]

Medication counting is another way to measure adherence. Classically referred to as "pill counting", in ophthalmology it is translated to the weight of the bottle. This is a simple, economical and non-invasive method. The main disadvantages of this method are: 1. The application of the medication can not be confirmed (it could have been intentionally thrown or instilled out of the eye) and 2. It depends on the subject bringing back the medication. [55, 56]

For the purposes of this study, the evaluation of the adherence will be favored by means of the diary of the subject, and will be carried out in the following way:

$$Ad = (A_r)100/A_i$$

Ad = Adherence

Ar = Registered applications

Ai = Applications indicated for the IP

The final adhesion will be determined by the average of the adherence of each one of the visits. Overall adherence (all subjects) will be determined by the average final adherence of each of the subjects.

6.3.3 6.3.3 Treatments and concomitant medications allowed and prohibited during the study.

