- Urine pregnancy test: Refers to the performance of a rapid pregnancy test in all women of childbearing age who wish to enter the study. By fertile age we understand women who have presented their menarche and have not presented their menopause. Menopause is defined as 12 months from the last menstruation in women over 40 years of age; or those who underwent bilateral hysterectomy or oophorectomy. Women of childbearing age with contraceptive methods including bilateral tubal obstruction should be tested for pregnancy. This test will be done by the PI or the designated team person according to the instructions of the device delivered by the sponsor.
- Vital signs: see 6.4.3.7 Vital signs.
- Visual capacity: see 6.4.3.1 Visual capacity.
- Comprehensive ophthalmological evaluation: see 6.4.3.2 Comprehensive ophthalmological evaluation.
- Integrity of the ocular surface: see 6.4.3.4 Integrity of ocular surface:
- Intraocular pressure: see 6.4.3.6 Intraocular pressure.
- Eligibility criteria: refers to the review by the PI, where it states that the subject can be included in the study by meeting the inclusion criteria and not meeting the exclusion criteria. See 6.2.1 Selection criteria.
- Sampling of laboratory samples: see 6.4.3.8 Laboratory tests.
- Adverse events: see 6.4.3.5 Presence of adverse events.

6.5.1.2 Basal visit.

- Review of laboratory tests: refers to the review and analysis by the PI of the results of the BH, QS and PFH.
- Eligibility criteria: with the results of the laboratory the profile of the subject will end for its inclusion or not.
- Evaluation of variables: The data of the evaluation of the variables listed below can be taken from the scrutiny visit. It is the prerogative of the PI to decide whether to use the information from the screening visit or to repeat the evaluations in this visit.
 - Intraocular pressure
 - Visual capacity
 - Integrity of the ocular surface

- Comprehensive ophthalmologic evaluation
- vital signs
- Eye comfort index: see 6.4.3.3 Eye comfort index.
- Assignment of IP: Refers to determine the intervention that the patient will follow during the study. It will be done according to the Methods section. Assignment of the intervention. This assignment will be made at the baseline visit (day 1) and will go along with the indication to start the treatment period at night.

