Calculation: the percentage of AD presented in the group treated with travoprost was considered. Expecting a similar proportion of conjunctival hyperemia due to PGA and healthy subjects. Considering a power of 80%, a significance level of 0.05 (α) and a non-inferiority margin of 5% (δ).

Calculated sample: 20, increasing the calculation by 20% considering possible losses, 25 subjects.

Suggested sample: 12 subjects (24 eyes) per treatment arm.

6.7 Recruitment.

It is essential that, if necessary during the development of this research protocol, the principal investigator requests the approval of the Research Ethics Committee and the Research Committee, as well as the authorization of COFEPRIS, to publish or disseminate in mass media, the invitation to participate in the study to those people who meet the selection criteria.

It is possible to discuss with other health professionals the opportunity for healthy subjects to be evaluated by an ophthalmologist at no cost, as well as cabinet exams that will allow the more accurate determination of their ocular clinical status by participating in a sponsored clinical research protocol by Sophia Laboratories, SA of C.V.

7 Methods. Assignment of the intervention.

7.1 Generation of the allocation sequence.

Two strata corresponding to the intervention groups will be used, which will be balanced for a research center. The allocation will be 1: 1. The generation will be carried out by a third party, authorized by Sophia Laboratories, S.A. of C.V., through its electronic system. The information corresponding to this third party will be found in the file.

7.2 Blinding mechanism.

Blinding will be done by the Department of Clinical Operations of Sophia Laboratories, S.A. of C.V. Which will consist of the elimination of the primary label (commercial) in the case of Travatan® and the placement of a label identical to the other IP. Because the bottle in which Travatan® is packaged differs in color and shape to that used for PRO-179, a masking will be made in the primary packaging which will be identical for the interventions. The subject will have determinedly prohibited to comment with another person that is not the pharmacist aspects related to the primary container (bottle).

7.3 Implementation.

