- Intra-group analysis: will be determined by the Wilcoxon rank test, for quantitative variables [65]
- Inter-group analysis: will be determined by the Mann-Whitney U test Kruskal-Wallis. This non-parametric test will be used to test whether a group of data comes from the same

population. Intuitively, it is identical to the ANOVA with the data replaced by categories using the student's t statistic.

The level of difference to consider significance will be an alpha of 0.05 or less.

The result of nominal and ordinal qualitative variables will be presented in frequencies, proportions and percentages, see table 3 (section 6.4.3).

The statistical analysis to identify significant differences of the qualitative variables will be done creating 2x2 contingency tables and it will be done in the following way:

- Intra-group difference: McNemar test [66]. Which is applied to 2×2 contingency tables with a dichotomous trait, with pairs of matched subjects, to determine if the marginal frequencies of row and column are equal (marginal homogeneity).
- Inter-group difference: Pearson's χ^2 test (or Fisher's exact).

The level of difference to consider significance will be an alpha of 0.05 or less.

For the reporting of adverse events all eyes of those participants who were randomly assigned to an intervention group after the baseline visit will be considered. The results will be expressed in number of cases (eyes).

The final report of the results will be shown in tables or graphs, as appropriate.

It will be considered that the investigational drug is safe and tolerable when there are no clinical and statistical differences in all the variables of primary outcome, with respect to its comparators.

Those subjects who comply with an adherence greater than 60% will be included in the statistical analysis to meet the objective of the study, taken from the subject's diary. It was considered that from the minimum dose necessary to obtain a pharmacological effect (hypotensive / 1 application per day) and the presence of adverse events (exposure) is sufficient to meet the overall design objective, according to the pharmacological characteristics of the IP.

8.3.2 Additional analyzes.

No additional analyzes are contemplated to those previously described. Nevertheless, these may be performed if during the conduction of the study it is required to analyze specific safety aspects of any intervention, maintaining the blinding until the end of the study.

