8.3.3 Population analysis and management of missing data.

An intention-to-treat analysis will be carried out, where the data of the participants who have completed the Visit 1 will be included.

9 9 Methods. Monitoring.

9.1 Data monitoring.

Monitoring visits by a monitor from Sophia Laboratories, S.A. of C.V. are intended to confirm that the studies sponsored by Sophia Laboratories, S.A. of C.V. they are conducted in accordance with the ethical principles that have their origin in the Declaration of Helsinki and that are consistent with the Good Clinical Practices and with the applicable regulatory requirements.

The researcher must ensure that they have sufficient time, space and qualified personnel for the monitoring visits.

Sophia Laboratories, S.A. of C.V. will monitor the study to verify, among other things, that:

- The data is authentic, correct and complete.
- They are protecting the security and rights of the subjects.
- The study is being carried out in accordance with the currently approved protocol, any other study agreement, Good Clinical Practices and all applicable regulatory requirements.

The details of the monitoring are documented in the Monitoring Plan (PM). The PM describes: the frequency and level of detail with which the monitoring will be performed, the activities to be carried out during the study according to its role (blind / non-blinded), the description of deviations from the protocol and its management.

9.2 Adverse events.

9.2.1 Responsibilities of the researcher.

Perform the verification of adverse events through questioning, review of the information recorded in the journal of the subject, relevant physical examination, assessment of evolution, as well as the appropriate medical and pharmacological management, resolution or outcome and final discharge following the definitions determined in the national and international regulations. [67] [68] [69]

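### Three analysis sets are described and none is assigned to the primary adverse-event comparison; the only one specific to adverse events has no dosing condition

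*Combined protocol and SAP*

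**What the plan says.** All references are to the combined protocol and SAP. Incidence of adverse events is a primary outcome, assessed on days 5, 11 and 14 (synopsis; section 6.4.1.1).

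Three rules bear on who is counted:

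- **Section 8.3.1, adverse-event reporting.** "all eyes of those participants who were randomly assigned to an intervention group after the baseline visit will be considered". Cases are counted in eyes.
- **Section 8.3.1, later.** "Those subjects who comply with an adherence greater than 60% will be included in the statistical analysis to meet the objective of the study". Section 6.3.2.1 computes adherence from the diary, with the numerator "Ar = Registered applications" and the applications indicated as the denominator.
- **Section 8.3.3.** "An intention-to-treat analysis will be carried out, where the data of the participants who have completed the Visit 1 will be included".

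The decision rule is also in section 8.3.1: "It will be considered that the investigational drug is safe and tolerable when there are no clinical and statistical differences" on the primary outcomes.

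Section 6.5.1.2 places assignment at the baseline visit and says that it "will go along with the indication to start the treatment period at night". Assignment therefore comes before the first drop. Section 8.3.3 has missing data in its heading but gives no rule for it.

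**The concern.** A subject can be assigned on day 1 and leave before instilling anything. Under the adverse-event sentence that subject stays in the denominator and can have no product-related event, so the arm's incidence is diluted. In a trial that concludes safety from the absence of a difference, dilution matters more than it would in a superiority trial. One subject is 1/12, or about 8%, of an arm.

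The other two rules carry a different risk. Someone who stops the drops because of an adverse event may fail the adherence threshold or never complete Visit 1. That is the subject a safety comparison most needs to keep. With no set named for the comparison, the choice could be made after the data are seen.

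**Working it through.** **1. What each rule does with two kinds of subject.**

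| Rule | Randomised, never dosed | Dosed, stopped early because of an event |
|---|---|---|
| All randomised (8.3.1) | kept | kept |
| Adherence above 60% (8.3.1) | 0 applications, 0%, excluded | can be excluded |
| Completed Visit 1 (8.3.3) | normally excluded | excluded if they leave before Visit 1 |

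Example for the adherence rule, assuming all 10 applications stay in the denominator after stopping. A subject who stops after 4 drops scores 4/10 = 40% on a simple count. Averaging over visits as in section 6.3.2.1, with 4 applications before Visit 1 and 6 after, the score is (4/4 + 0/6)/2 = 50%. Both are below the threshold. The plan does not say whether applications after stopping still count as indicated.

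**2. Inputs.** There are 12 subjects per arm (section 6.6.1). The rates are 41.9% (any ocular adverse event) and 12.9% (conjunctival hyperemia), both from the travoprost group cited there. They are used because entering them as the two arms reproduces the plan's calculated sample: (0.129 × 0.871 + 0.419 × 0.581) × ((1.645 + 0.842)/(0.129 − 0.419 − 0.05))² = 19.03, rounded up to 20, and 20/0.8 = 25. Whether those inputs suit the sample size is a separate matter.

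The plan gives no non-dosing rate. The nearest figure comes from "increasing the calculation by 20% considering possible losses", and 20% of 12 is 2.4 per arm, but that covers losses of every kind. Zero to two undosed per arm is therefore an assumption.

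**3. Dilution.** With m undosed subjects kept as non-cases, the expected incidence is multiplied by (12 − m)/12. With one undosed per arm, 41.9% becomes 41.9 × 11/12 = 38.4% and 12.9% becomes 11.8%. The difference falls from 29.0 to 26.6 points.

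**4. Chance that a two-sided Fisher test, by subject, gives p ≤ 0.05** (test arm 41.9%, reference 12.9%, exact enumeration):

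| Undosed (test, reference) | All randomised | Dosed only |
|---|---|---|
| 0, 0 | 20.7% | 20.7% |
| 1, 1 | 17.0% | 17.0% |
| 2, 2 | 13.5% | 13.5% |
| 1, 0 | 15.3% | 28.1% |
| 2, 0 | 10.8% | 21.7% |
| 0, 1 | 22.6% | 22.6% |
| 0, 2 | 24.8% | 24.6% |

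Equal numbers undosed leave the two sets alike at these rates. The gap opens when the undosed are in the higher-rate arm.

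**5. Average effect.** If each subject in either arm independently has an assumed 5% chance of never dosing, averaging over all outcomes gives about 19% for all randomised and about 22% for dosed only. Part of that gap is the discreteness of Fisher's test. In the table, removing one test-arm subject lifts the chance above the 20.7% obtained with everyone dosed. With 12.9% in both arms and one undosed in one arm, the rejection chance is 0.5% for all randomised and 1.2% for dosed only.

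**6. Single data sets, either direction.**

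- One undosed in the test arm: dosed only 6/11 v 1/12, p = 0.027; all randomised 6/12 v 1/12, p = 0.069.
- Two undosed in the reference arm: dosed only 9/12 v 3/10, p = 0.084; all randomised 9/12 v 3/12, p = 0.039.
- One undosed in each arm: dosed only 6/11 v 1/11, p = 0.064; all randomised p = 0.069. The verdict is the same.

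**The case against.** The strongest reply is that the all-randomised sentence governs how adverse events are reported. On this view the comparison that decides the trial is restricted to subjects above 60% adherence, where an undosed subject scores 0% and the effect is nil. That reading is available. But the all-randomised sentence is the only one of the three written for adverse events, and no passage ranks the rules. The reply therefore removes certainty about the dilution and leaves the ambiguity in place.

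A reader might infer that the plan treats undosed subjects as exposed, or scores unreached subjects as event-free. The documents say neither; they are silent on missing adverse-event status. Ascertainment is also partly covered. A missed appointment triggers a call, with adverse events asked as minimum data (sections 6.2.4 and 8.1.1). Early termination brings an unscheduled visit and then the security call (section 6.5.1.6).

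A reader might also infer a systematic pull towards the sponsor's conclusion. The reference-arm example above goes the other way, and balanced non-dosing barely matters. The 6/11 v 1/12 example is also a selected one. With one undosed test-arm subject, 12 × 13 = 156 tables are possible, and the verdict at 0.05 changes in 8. Finally, these figures are by subject, while the plan counts eyes. If both eyes were counted as independent, that same example would stay significant under the written denominator (12/24 v 2/24, p = 0.003). All of this limits the size of the point.

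**Conclusion.** The point holds as a minor defect of specification: three incompatible sets, and none assigned to the primary adverse-event comparison. The consequence depends on which rule is applied.

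- **All randomised.** Undosed subjects dilute incidence and, on average, modestly reduce the chance of detecting a difference: about 19% against 22% at 41.9% v 12.9% and 5% non-dosing. This assumes non-dosing is equally likely in both arms and the analysis is by subject. In a given imbalance the effect can go either way.
- **Adherence or Visit 1.** Undosed subjects are normally excluded, but subjects who stopped because of an adverse event can be lost. The documents give no basis for estimating how many.

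The documents do not support a stronger statement that the plan builds in a bias towards finding no difference.

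**What to change.** In section 8.3.1:

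1. Name one set for the adverse-event comparison: all randomised subjects with at least one recorded or reported application.
2. List randomised but undosed subjects separately.
3. Report a dosed subject with no adverse-event enquiry after the first drop as unknown, and add one sensitivity line counting that subject as an event.
4. State that the adherence set and the Visit 1 set of section 8.3.3 do not govern this comparison.

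This set keeps early stoppers and leaves out the undosed, so it deals with both risks. The diary, visits and calls already supply the data. The cost is a few sentences and one extra line of output. The downside is that the set is no longer strictly all-randomised, and the reported incidence may look slightly less favourable.

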At the counting stage, the participant number will be assigned consecutively, using 3 consecutive digits. Once the subject has been selected, he will be assigned a number with which he will be identified throughout the study. Said code will be composed of eight numbers in the following order from left to right:

- three digits of the molecule under study according to the denomination by the sponsor.
- two digits corresponding to the research center number.

- three digits of the number consecutive to its inclusion assigned to the research center.

Example:

6.3 Intervention.

The subjects will be divided into two equal groups, to which they will be assigned randomly and blinded to one of the products in research (PI) PRO-179 or Travatan®.

Dosage: 1 drop every 24 hours, at night, in both eyes.

Instructions for administration: instillate a drop in the conjunctival sac, it is recommended to exert gentle traction on the lower eyelid, with the index finger, to expose the cul-de-sac and instillation. Avoid blinking energetically for the next few minutes or closing your eyes in a forced way.

Duration of the intervention: 10 days.

6.3.1 Medications administered.

6.3.1.1 Drug under study.

- Generic name: Travoprost
- Distinctive denomination: Bristrio® (PRO-179)
- Active principles: Travoprost 0.004%.
- Pharmaceutical form: Ophthalmic solution
- Presentation: multi-dose dropper bottle, 2.5 ml.
- Prepared by: Sophia Laboratories, S.A. of C.V.
- Description of the solution: transparent solution, free of visible particles.
- Description of container: White bottle with 5mL capacity, made of low density polyethylene.

Agent	Quantity mg / mL	Function
Travoprost	0.040	Active principle
Hydroxypropylbetacyclodextrins	Not showing	Stabilizer
Mannitol	Not showing	Toning
Boric acid	Not showing	Buffer Agent
Sodium Borate Dehydrated	Not showing	Buffer Agent
Disodium edetate Dihydrate	Not showing	Chelating Agent
Benzalkonium Chloride (1)	Not showing	Conservative
Water for the preparation of Injectables c.b.p.	1.000 mL	Vehicle

Table 2. Quali-quantitative formulation of PRO-179

6.3.1.1 Reference medicine.

- Generic name: Travoprost
- Distinctive denomination: Travatan®
- Active ingredients: Travoprost 0.004%
- Pharmaceutical form: Ophthalmic solution.
- Presentation: multi-dose dropper bottle, 2.5 ml.
- Prepared by: Alcon Laboratories Inc.
- Description of the solution: transparent solution, free of visible particles.
- Consult information to prescribe.

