The return will be made by the research center when the sponsor indicates it. Prior to the return, the research center must make a count of the assigned medication and the remaining medication, with the aim of creating an inventory which serves for the final filling of the medication return form.

6.4 Delay variables.

6.4.1 Security variables.

6.4.1.1 Primary outcome variables.

- Incidence of adverse events.

6.4.1.2 Variables of primary outcome of tolerability.

- ICO score.

6.4.1.3 Secondary outcome variables.

- Changes in visual ability.
- Changes in corneal and conjunctival staining with lysine green.
- Changes in corneal and conjunctival staining with fluorescein.
- Changes conjunctival hyperemia.
- Incidence of chemosis.
- Incidence of alterations in the results of laboratory tests.
- Incidence of alterations in the FC.
- Incidence of alterations in the RF.
- Incidence of alterations in the TAS.

6.4.2 Exploratory variables.

- Changes in IOP.

6.4.3 Methods and scales to be used for the measurement of the variables.

Variable	Kind	Unit (Symbol)	Method of measurement	Normal value	Evaluation time	Statistical test
Primary						
Adverse events	Discreet Categorical rating	Number of cases (n) Present/absent	Count Observation	0 Absent	VB, V1, VF y LLS	Mann-Whitney U χ^2 o Fisher's exact
ICO score	Discreet	Points	Questionnaire	NA	VB, VF	Mann-Whitney U
Secondary						
Visual ability	Discreet	Fraction	Snellen Primer	1	VB, V1 y VF	Mann-Whitney U
Corneal and conjunctival staining with fluorescein	Ordinal	Degrees	Direct observation with slit lamp and cobalt blue filter, Oxford scale graduation	0	VB, V1 y VF	χ^2 or Fisher's exact

Variable	Kind	Unit (Symbol)	Method of measurement	Normal value	Evaluation time	Statistical test
Corneal and conjunctival staining with lysamine green	Ordinal	degrees	Direct observation with slit lamp, Oxford scale graduation	0	VB, V1 y VF	χ^2 or Fisher's exact
Conjunctival hyperemia	Ordinal	Normal / Very Light / Mild / Moderate / Severe	Direct observation. Classification of Efron.	Normal	VB, V1 y VF	χ^2 or Fisher's exact
Chemosis	Categorical rating	Present / absent		Absent	VB, V1 y VF	χ^2 or Fisher's exact
FC	Discreet	eats per minute (l / m)	Auscultation with stethoscope	60 to 100	VB, V1 y VF	Mann-Whitney U
FR	Discreet	Breaths per minute (r / m)	Auscultation with stethoscope	12 to 24	VB, V1 y VF	Mann-Whitney U
TAS	Discreet	Millimeters of mercury (mmHg)	Measurement with sphygmomanometer	90-120/ 60-80	VB, V1 y VF	Mann-Whitney U

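### Section 8.3.1 counts the primary adverse-event outcome in eyes although subjects are randomised and treat both eyes; it sets no subject-level unit for the comparison and no method for paired eyes.

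*Combined protocol and SAP*

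**What the plan says.** Section 6.3 makes the subject the unit of randomisation: "The subjects will be divided into two equal groups, to which they will be assigned randomly". The same section has each subject treat both eyes with the assigned product: "Dosage: 1 drop every 24 hours, at night, in both eyes". Section 6.6.1 gives the size as 12 subjects, or 24 eyes, per arm.

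Section 8.3.1 defines the adverse-event set by eye: "For the reporting of adverse events all eyes of those participants who were randomly assigned". The next sentence gives the unit: "The results will be expressed in number of cases (eyes".

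The between-group tests in 8.3.1 are Mann-Whitney U for quantitative variables and Pearson chi-square or Fisher's exact test for qualitative ones. The analysis "of the qualitative variables will be done creating 2x2 contingency tables". The paired methods named, Wilcoxon and McNemar, are for intra-group differences. McNemar is described as working "with pairs of matched subjects, to determine if the marginal frequencies of row and column are equal"; it is not offered for the two eyes of one person.

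Table 3 (section 6.4.3) lists adverse events as "Number of cases (n) Present/absent", with Mann-Whitney and chi-square or Fisher, and does not say whether a case is an eye or a subject.

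**The concern.** Chi-square, Fisher and Mann-Whitney all assume independent observations. Two eyes of one person on the same drop share the drug, the person and the examiner, so their outcomes will tend to agree. Entering 24 eyes per arm as 24 independent units overstates the information. Confidence intervals become too narrow, and differences are declared too often when none exists.

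This bears on the trial's conclusion. Section 8.3.1 calls the product "safe and tolerable when there are no clinical and statistical differences in all the variables of primary outcome". On the same data, the statistical part of that rule can change with the unit chosen, and the section does not fix the unit for the test. An eye count also has no place for systemic events, which section 9.2.1.3 says may occur.

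The same gap affects hyperemia, staining, chemosis, visual ability and intraocular pressure. Visual acuity, for example, is taken in each eye (6.4.3.1), but no unit of analysis is stated. The other primary outcome, the ocular comfort index, is one questionnaire per subject and is not affected.

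**Working it through.** **Inputs from the documents.** 12 subjects per arm, both eyes treated: 12 × 2 = 24 eyes per arm, as section 6.6.1 states, and 48 in all. Significance level 0.05 (8.3.1), taken as two-sided. Reference rates from 6.6.1: ocular adverse events in 13/31 = 41.9% of travoprost patients, and hyperemia in 12.9%. These are rates per patient.

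**Assumed.** The documents give no between-eye correlation ρ. I use 0.5-0.9 and also look below that range.

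**Rough size.** With two eyes per subject, the variance of an arm's eye proportion is inflated by 1 + ρ. At ρ = 0.5 the 24 eyes carry the information of 24/1.5 = 16 independent eyes; at ρ = 0.9, 24/1.9 = 12.6.

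**Exact calculation.** For per-eye rate p, a subject has both eyes affected with probability p² + ρp(1−p), and exactly one with probability 2p(1−p)(1−ρ). Example at p = 0.129, ρ = 0.5: p(1−p) = 0.1124, so both = 0.0166 + 0.0562 = 0.0728, one = 0.1124, none = 0.8148. Convolve over 12 subjects per arm with the same p in both arms. Then sum the probability of every 24 v 24 table that the test rejects at p ≤ 0.05.

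To keep the rates in 6.6.1 as per-patient rates s (at least one eye affected), solve s = 1 − [(1−p)² + ρp(1−p)] for p. Check at s = 0.129, ρ = 0.5: p = 0.0886 gives 1 − (0.8306 + 0.0404) = 0.129.

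| Rate held fixed | ρ | Per-eye p | Fisher | Pearson, uncorrected |
|---|---|---|---|---|
| 12.9% of patients | 0.5 | 8.9% | 4.4% | 9.7% |
| | 0.8 | 10.9% | 7.6% | 15.8% |
| | 0.9 | 11.9% | 8.4% | 18.6% |
| 41.9% of patients | 0.5 | 31.2% | 7.2% | 11.7% |
| | 0.8 | 37.2% | 10.4% | 15.7% |
| | 0.9 | 39.5% | 11.7% | 16.8% |
| 12.9% of eyes | 0.5 | 12.9% | 6.1% | 11.5% |
| | 0.9 | 12.9% | 9.0% | 18.7% |
| 41.9% of eyes | 0.5 | 41.9% | 7.5% | 12.3% |
| | 0.9 | 41.9% | 11.8% | 16.9% |
| 5% of eyes | 0.5 | 5% | 1.7% | 5.3% |
| | 0.9 | 5% | 2.4% | 10.6% |

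For reference, with independent eyes (ρ = 0) at 12.9% and 41.9% of eyes, Fisher is 2.2% and 2.8%, and Pearson 5.3% and 5.7%. At ρ = 0.25 Fisher is 4.0% and 5.0%, and Pearson 8.2% and 9.0%. Fisher's own conservatism therefore absorbs a mild correlation; Pearson has no such reserve.

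**Same data, two units.** Suppose every event is bilateral, with 1/12 v 5/12 subjects affected. By subject, Fisher gives p = 0.155 and the difference is 4/12 = 33 points (Newcombe 95% CI −2 to +61). By eye, 2/24 v 10/24 gives p = 0.017 (CI +9 to +54). Of the 78 unequal all-bilateral splits of 12 v 12, 30 are significant by subject, 17 more only by eye, and none only by subject. All-bilateral is the extreme case (ρ = 1).

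**The case against.** The strongest reply is that the eye sentence governs reporting. It says which eyes are counted and how results are expressed, and it does not say that the tests use eyes as the denominator. Table 3, which assigns the tests, names no unit. The adherence rule in 8.3.1 and the analysis population in 8.3.3 are worded by subject or participant, and the adverse-event record (9.2.1.1) is keyed to the patient, with eye as an attribute. This stands: a reader might infer that the plan prescribes testing 24 v 24 eyes, and the text does not say so. The gap remains all the same, because the eye is the only adverse-event unit that 8.3.1 gives. A Mann-Whitney test on a count per subject would be valid, but the plan does not specify one.

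A reader might also infer that no participant-level count appears anywhere. Section 10.3 has one, for serious events in more than 10% of participants, but it is a criterion for suspending or ending the study, not the primary comparison.

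Nor do the documents support saying that the error certainly exceeds 5%. That depends on an assumed correlation and on the event rate. The rates in 6.6.1 come from glaucoma patients followed for up to 12 weeks, while this trial treats healthy subjects for 10 days. Section 5.2.3 does cite hyperemia in 27-49%, so rates in the upper part of the range are not arbitrary.

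Finally, inflation of this kind favours a false difference, not a false finding of safety. The rule in 8.3.1 also includes a clinical judgement and does not make the test the sole condition.

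**Conclusion.** The point holds as a gap in 8.3.1. The primary adverse-event outcome is expressed in eyes, the subject is the randomised unit, and neither a subject-level unit for the comparison nor a method for paired eyes is given. That the tests would be run on eyes is the natural reading, but an inference.

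On that reading, with the rates in 6.6.1 kept per patient and ρ assumed at 0.5-0.9, type I error is about 4-12% for Fisher and 10-19% for uncorrected Pearson. If those rates are read per eye instead, the figures are 6-12% and 12-19%. At 5% of eyes Fisher is about 2% and Pearson about 5-11%. The consequences are false findings of difference and overstated precision. This should be fixed before analysis. Confidence is medium, because the unit of the test is inferred and the correlation is assumed.

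**What to change.** State in 8.3.1 that the subject is the unit for the between-group adverse-event comparison. Compare subjects with at least one adverse event, in either eye or systemic, by Fisher's exact test on 12 v 12. Alternatively, use a test clustered on subject, such as an exact permutation of subjects on 0, 1 or 2 affected eyes, with systemic events then compared by subject separately. Report the difference in subject incidence with its 95% confidence interval, and keep eye counts as a descriptive listing. For hyperemia, staining, chemosis, visual ability and intraocular pressure, pre-specify one value per subject or a method clustered on subject.

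No new measurement is needed: the adverse-event record already holds subject code, left eye and right eye (9.2.1.1). The cost is in apparent size and power. The count falls from 48 eyes to 24 subjects. Fisher on 12 v 12 is conservative, with type I error about 0.5% at a subject rate of 12.9% and 2.2% at 41.9%, and has about 21% power for 12.9% v 41.9%. The permutation test has about 23-24% at the same subject rates with ρ of 0.5-0.9. Fisher on eyes would show 43-51% there, but without control of its error rate.
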